9.0 Procedures Involved

9.1 Study design:

The clinical trial will be an assessor-blinded prospective randomized cross-over trial wherein participants with unilateral transfemoral amputation will be randomized to using one of two socket conditions (i.e., sub-ischial or ischial containment) before crossing over to the other socket condition. Random allocation (computer-generated) utilizing blocks of random size will be used to assign the initial treatment condition. The trial will be balanced such that all subjects will receive all treatments (i.e., both socket conditions) and that all subjects will participate for the same number of periods (i.e., two).

9.2 Research procedures:

The study is composed of two phases for each socket: socket preparation and then 6 weeks of socket wear during which 3 identical data collection sessions will be held (week 1, 3 weeks and 6 weeks).

Socket Preparation Phase:

All sockets will be made following standard clinical procedures that include taking an impression (i.e., cast) of the residual limb, converting the negative residual limb model to a positive mold made of plaster of Paris, rectifying the positive mold using the rectification procedures specific to each socket design, thermoforming a clear diagnostic check socket, and ultimately manually fabricating, fitting and aligning a definitive socket.

Data Collection:

At each visit we will collect the following data:

1. *Socket Comfort Score (SCS)* – The SCS is a simple rating of comfort on a scale of 0 to 10 where 0 is the most uncomfortable socket fit imaginable and 10 is the most comfortable socket fit.
2. *Orthotic and Prosthetic Users' Survey (OPUS)* – The OPUS is a set of surveys that evaluate the subject's perception of function, quality of life, and satisfaction with the socket and prosthesis. The lower extremity function survey has 20 questions rated on a 5-point scale; the quality of life survey has 23 questions rated on a 5-point scale; and the satisfaction with device survey has 9 questions rated on a 5-point scale.

PROTOCOL TITLE: Functional Performance Evaluation of the Northwestern University Flexible Sub-Ischial Vacuum (NU-FlexSIV) Socket for Persons with Transfemoral Amputation

3. *Biomechanics of Walking* – How the subjects walks with each socket will be measured in a computerized motion analysis lab. Small reflective markers are taped to anatomical landmarks on the legs, pelvis and arms using hypoallergenic tape. The subject then walks back and forth at their own comfortable walking speed while cameras on the wall record where the reflective markers are in space and force plates mounted flush in the floor measure the force applied by each foot.
4. *5-Time Rapid Sit-to-Stand Test (RSTS)* - The RSTS measures hip range of motion, lower limb muscle strength, and balance. The test involves measuring the time it takes for the subject to stand up and sit down five times with their arms folded across their chest as fast as they can. They will do this test twice with 3 minutes of rest in between each test.
5. *Four-Square-Step Test (FSST)* - The FSST evaluates dynamic standing stability and involves rapid stepping in different directions over an obstacle. The obstacle consists of a square cross made by resting four sticks flat on the floor. A stepping pattern is demonstrated to the subject and then one practice trial is allowed to ensure that they understand the pattern. They must try to complete the stepping pattern as fast as possible without touching the sticks. Both feet must make contact with the floor in each square. If possible, the subject must face forward during the entire test. They will do this test twice with 3 minutes of rest in between each test.
6. *T-Test of Agility (T-Test)* - The T-Test is typically used by athletes to test movement agility. Four markers are set out on the floor in the shape of a T. The subject starts at the marker located at the bottom of the T. When the investigator says “go” the subject moves forward as fast as they can to touch the second marker, they then shuffle sideways to the right to touch the third marker, and then they shuffle to the left, past the second marker, to touch the fourth marker. The subject then shuffles back to their right to touch the second marker and then moves backwards as fast as they can to touch the first marker. The test is timed and should be performed as fast as possible. The test is repeated three times and the best time is used. The subject will be allowed to rest for 3 minutes between tests.

9.3 (a) Procedures performed to lessen the probability or magnitude of risks:

All socket fabrication procedures used in this study are consistent with standard clinical care procedures. The standard clinical process of making a transfemoral prosthetic socket involves some loss of modesty and privacy given the intimate fit of the standard-of-care Ischial Containment socket with your groin and buttocks. Certified Prosthetists are trained to ensure privacy during this process. Risk is further minimized by recruiting subjects who have used a prosthesis for at least two years and are therefore familiar with the process.

PROTOCOL TITLE: Functional Performance Evaluation of the Northwestern University Flexible Sub-Ischial Vacuum (NU-FlexSIV) Socket for Persons with Transfemoral Amputation

It is possible that one or both sockets may not be comfortable or that one or both sockets may rub the residual limb and cause redness, blistering, or a sore, just as any new or ill-fitting socket may do. Inclusion/exclusion criteria will help minimize the risk of these problems by only allowing persons to participate who have used a prosthesis for at least two years, have a residual limb that is stable in volume and free from any wounds and no skin/residual limb issues that make fitting a socket problematic. Subjects will actively contribute to minimizing residual limb problems by checking their limb each day, informing investigators of problems as soon as they occur, and working with the study prosthetists to resolve any issues.

Transfemoral amputees are generally at greater risk for stumbling, tripping and falling than people who are not amputees. The risk of stumbling, tripping and falling may be increased while performing some of the mobility tests used in this study. All tests are standardized clinical outcome measures used with amputees and will be performed under controlled lab conditions to ensure that the subject is not distracted from the task and that all other conditions such as ambient lighting, floor surfaces, etc. are favorable, helping minimize risk. Subjects are asked to perform some of the tests “as fast as they can” rather than pushing them to exceed their own comfortable limits, further serving to minimize risk.

(b) Devices used in this research, the purpose of their use, and their regulatory approval status:

Two designs of custom made prosthetic sockets will be compared in this research: (1) the Ischial Containment (IC) Socket and (2) the NU-FlexSIV Socket (Figure 5).

The standard-of-care IC socket design will be determined on a per-subject basis by the Certified Prosthetist using standard clinical practice procedures. However, subject selection criteria will serve to decrease the variability in patient presentation such that it will minimize the choice of suspension options. Therefore, the IC socket will consist of a flexible inner socket with rigid frame using either skin fit suction suspension with a one way valve or silicon liner with locking mechanism. If a liner is used it will be sized according to manufacturer recommendations.

The NU-FlexSIV Socket will also be custom fit to each subject using standard clinical practice procedures. Subischial socket trim lines are typically 25mm distal to the ischial tuberosity and 50mm distal to the greater trochanter and while it also has a narrower medio-lateral than

Figure 5 Ischial Containment Socket (left) and NU-FlexSIV Socket (right).

PROTOCOL TITLE: Functional Performance Evaluation of the Northwestern University Flexible Sub-Ischial Vacuum (NU-FlexSIV) Socket for Persons with Transfemoral Amputation

anterior-posterior dimension, it has a more rounded cross-sectional profile than the IC socket. All subjects will be fit with an undersized liner (i.e., liner one size smaller than the manufacture recommendation based on measurements) over which the sub-ischial socket will be fitted. Using the rectification procedures specific for this design, sockets are also 4-6% undersized. Suspension will be achieved using an Össur Unity mechanical vacuum pump.

With the exception of the prosthetic foot, prosthetic components distal to the socket (the knee and pylon) will be standardized within subjects. Subjects will use their current prosthetic knee so as to minimize the burden of learning to walk with a different knee. All subjects will be provided an Össur LP Variflex foot with Unity Pump to wear with both test sockets. This foot is suitable for K3 and K4 ambulators⁵² and can interface with any existing componentry while also providing a noiseless vacuum pump for use with the sub-ischial socket condition.

The purpose of both sockets is to restore the ability to walk for someone with a transfemoral amputation. Prosthetic sockets form the interface between the residual limb and prosthesis, allowing for support of body weight and transfer of forces between the amputee and the prosthesis.

The type of external limb prosthesis we propose to evaluate as part of this clinical trial is considered by the Food and Drug Administration (FDA) as a Class I device (low risk) and 510k exempt (although not necessarily IDE exempt). As part of our current IRB approval for a pilot study with the same device (STU00033446), a determination was made by the FDA that our device was not a custom device, necessitating that the Northwestern University Institutional Review Board (NU-IRB) make a significant risk determination. The NU-IRB made a determination that the use of the device constituted a non-significant risk, which meant that we did not have to apply for an Investigational Device Exemption from the FDA.

According to FDA regulation 21CFR890 (External Limb Prosthetic Component) our device meets that requirement but does not have an automatic exemption. Hence, whether our device is subject to FDA regulation for this proposed work depends upon NU-IRB determination of whether the device as proposed for use in this study is a significant risk device. If the NU-IRB determines as it did previously for a similar smaller pilot study that our device constitutes a non-significant risk, then we will not be subject to FDA regulation and will not need to apply for an IDE.

According to FDA requirements, as the manufacturer of the device, the Principal Investigator (PI) can make the determination that this is a non-significant risk device. The subsequent IRB determination will either support the PI's decision or override it and require that an IDE application be submitted to the FDA. Hence, based on previous experience regarding FDA and IRB determinations and recent correspondence with NU-IRB regarding this issue (see attached), the PI has determined that the device to

PROTOCOL TITLE: Functional Performance Evaluation of the Northwestern University Flexible Sub-Ischial Vacuum (NU-FlexSIV) Socket for Persons with Transfemoral Amputation

be used in this study constitutes a non-significant risk and hence an IDE is not required and has not been applied for. We are aware that this determination is subject to change based on review by NU-IRB.

(c) Source records that will be used to collect data about subjects:

All data needed for this study will be collected directly from the subjects. Included in the eIRB+ application are the Subject Information Form, Socket Measurement Forms, OPUS and AMP data collection forms.

9.4 Data to be collected:

- *Patient Characteristics:* age, height/weight, time since amputation, etiology of amputation, residual limb length, residual limb tissue type (soft, medium, firm), hip flexion contracture magnitude, current prosthesis description, Socket Comfort Score in existing socket, and Medicare Functional Classification Level assessed using the Amputee Mobility Predictor (AMP).
- *Socket Measurements:* See Socket Measurement Forms in eIRB+ application.
- *Patient-Reported Outcomes:* Socket Comfort Score and OPUS.
- *Functional Performance Measures:* biomechanics of gait, 5-times Rapid Sit-to-Stand Test, Four Square Step Test, T-Test of Agility.

9.5 For HUD uses provide a description of the device, a summary of how you propose to use the device, including a description of any screening procedures, the HUD procedure, and any patient follow-up visits, tests or procedures:

N/A

10.0 Data and Specimen Banking

10.1 Data or specimens banking for future use:

Specimens are not applicable.

The investigators will retain all data recorded during the study. Any electronic data maintained at NUPOC is on encrypted and password protected computers in locked rooms and paper files are stored in locked cabinets in locked rooms. Both computers and paper files are accessible only to NUPOC personnel. Data will not be destroyed.

De-identified data will be entered into RedCap for analysis by the statistician.

10.2 Data to be stored or associated with each specimen:

N/A

10.3 Procedures to release data or specimens:

PROTOCOL TITLE: Functional Performance Evaluation of the Northwestern University Flexible Sub-Ischial Vacuum (NU-FlexSIV) Socket for Persons with Transfemoral Amputation

N/A

11.0 Data and Specimen Management

11.1 Data analysis:

Before analyses begin, all variables will be plotted using histograms to inspect the shape of distributions and to check for outliers. We will not drop cases nor transform variables but if we identify any possibility that assumptions have been violated, we will employ alternative analysis approaches. As part of data screening, we will describe the amount of data that are missing, and we will compare participants with and without missing data.

Hypothesis 1: We hypothesize that the NU-FlexSIV Socket will provide increased comfort compared to the ischial containment socket.

Our primary end point is Socket Comfort Score at 6 weeks, which has been reported to have a sensitivity to socket change of 1 to 3 points (Hanspal, Fisher et al. 2003). Additionally, it has been argued that the Socket Comfort Score may be considered a continuous variable, and therefore suitable for parametric analysis, given the large number of ordered categories and the linear nature of changes in socket comfort with different configurations of socket conditions (Fatone, Dillon et al. 2015). Hence, a matched pairs t-test ($\alpha=0.05$) will be used to assess the primary outcome, Socket Comfort Score.

Hypothesis 2a: We hypothesize that the NU-FlexSIV Socket will allow greater prosthetic side hip range of motion, in particular increased hip extension, leading to increased prosthetic side step length and hence walking speed compared to the ischial containment socket.

Hypothesis 2b: We hypothesize that step width and lateral trunk flexion over the prosthetic limb will not differ between the NU-FlexSIV Socket and ischial containment socket.

For these secondary hypotheses, data analysis will include the following gait variables: walking speed (m/s), step width (m), step length (m), sagittal plane hip range of motion (degrees), maximum hip extension (degrees), and lateral trunk lean over the prosthetic limb during stance (degrees). A multiple analysis of variance (MANOVA, $\alpha=0.05$) will be used to compare gait variables across socket conditions as it is the most rigorous approach given the relationship that exists between these dependent variables (e.g., walking velocity and step length are correlated). The challenge of this approach is being convinced that underlying assumptions are met.

Hypothesis 2c: We hypothesize that the NU-FlexSIV Socket will result in faster times to perform the 5-Times Rapid Sit-to-Stand Test, Four Square Step Test and T-Test of Agility compared to the ischial containment socket.

PROTOCOL TITLE: Functional Performance Evaluation of the Northwestern University Flexible Sub-Ischial Vacuum (NU-FlexSIV) Socket for Persons with Transfemoral Amputation

The difference in these timed performance tests across socket conditions will be tested using repeated measures t-tests with alpha=0.05 which will be adjusted using the Bonferroni correction to account for Type 1 error.

Hypothesis 3: We hypothesize that the NU-FlexSIV Socket will result in better health-related quality of life and satisfaction with device as assessed using the OPUS compared to the ischial containment socket.

The OPUS uses Likert scale responses for each item of each module. However, these responses can be converted into a single score for each module. If assumptions of normality are met, analysis with parametric procedures can be used to assess differences in module scores between sockets. Hence, we will use repeated measures t-tests with alpha=0.05 which will be adjusted using the Bonferroni correction to account for Type 1 error.

11.2 Power analysis:

To determine a sample size estimate, we have utilized data obtained from a previous pilot study.⁴⁴ In that study, we collected Socket Comfort Scores from six persons with unilateral transfemoral amputation wearing an ischial ramal containment socket and the same socket with a wider medio-lateral dimension (effect size, $d = 0.754$). Using the G*Power computer program, this effect size was used to estimate sample size. This data was used because we do not have pilot data for this particular study design. For a 2-tailed matched pairs t-test we would need a total sample size of 25 to detect an effect size of 0.754 with a critical alpha of 0.05 and power of 0.95. In order to account for possible attrition in subject numbers we will recruit 35 persons with unilateral transfemoral amputation.

11.3 Steps to be taken to secure the data to maintain confidentiality during storage, use, and transmission:

All personnel involved with the study have or will complete IRB required training.

Subjects will be assigned a study code at enrollment and all study related forms to be completed by our clinical collaborators will be labelled only with the study code. Forms that require the subject's identity and cannot be coded (e.g. payment paperwork) will only be completed at NUPOC and not at the clinical sites. The master list of study codes will be maintained at NUPOC by the PI. This master list will only be maintained in hard copy format, in a locked cabinet in the PI's office which is also locked.

The collaborating prosthetists will only create and use the forms required for recording the fitting and fabrication of their particular socket and these can be de-identified. Once the subject has completed that phase of the study, forms are given in person or by mail to the PI to collate with the main subject file to be held at NUPOC.

All electronic data maintained at NUPOC is on encrypted and password protected computers located in locked rooms and all paper files are stored in

PROTOCOL TITLE: Functional Performance Evaluation of the Northwestern University Flexible Sub-Ischial Vacuum (NU-FlexSIV) Socket for Persons with Transfemoral Amputation

locked cabinets in locked rooms. Both computers and paper files are accessible only to NUPOC personnel.

All data entered into RedCap will be de-identified summary data needed for statistical analysis.

11.4 Procedures to be used for quality control of collected data:

A cross-over study has two advantages over both parallel and non-crossover longitudinal study designs. First, the influence of confounding covariates is reduced because each cross-over patient serves as their own control. This is particularly important given the custom nature of prosthetic interventions. Second, cross-over designs can be statistically efficient, requiring fewer subjects than non-cross-over designs. This is of particular benefit for prosthetic studies given the cost, time and effort involved in providing custom prosthetic devices for use every day during the study. Cross-over studies are typically subject to order effects, which in this case the most likely is shrinking of the residual limb during the first intervention phase. This shrinkage is typical of what happens any time a new, more tightly fitting socket is provided to a person with amputation. However, the effect of shrinkage is accounted for by having casting and fabrication of the second test sockets occur after data collection in the first socket is completed. While a washout period is not strictly necessary, it is effectively included as subjects will need to transition back to their usual, pre-study socket/prosthesis while the second test socket is fabricated.

Socket allocation will be concealed from the investigators until after a subject is enrolled. The starting socket design will be enclosed in sequentially numbered, opaque, sealed envelopes. Envelopes will be opened sequentially and only after the participant's name and other details are written on the appropriate envelope.

Blinding of prosthetic interventions is challenging given that they are devices that must be custom-fabricated and donned each day by the subject. Hence, for this study only the assessor, our research engineer, [name], will be blinded. To maintain blinding the assessor will remain uninformed in any aspect of the study except administration of performance and patient-reported measures and processing motion analysis data.

- The assessor will not be present for motion analysis data collection given that this requires exposure of the prosthesis and socket for appropriate marker placement. Since all that is recorded is the location of retro-reflective markers on the subject, it is not

[figure not shown]

Figure 6 Motion analysis data processing window.

PROTOCOL TITLE: Functional Performance Evaluation of the Northwestern University Flexible Sub-Ischial Vacuum (NU-FlexSIV) Socket for Persons with Transfemoral Amputation

possible to tell while processing the motion analysis data what socket the subject was wearing because the data is viewed only as a stick figure (Figure 6).

- Performance and patient-reported measures can be administered fully clothed, which will disguise the socket being tested. During these assessments, subjects will be instructed not to reveal to the assessor which socket they are wearing.

Given the customized, manually-fabricated nature of prosthetic sockets, each test socket will be provided to study subjects by a separate Certified Prosthetist known for their skill with the particular socket design. This will ensure that each socket is the best and most consistent example of each particular socket design.

Since accommodation to sockets is unknown, data will be collected at baseline (within one week of definitive socket fitting) and after 3 and 6 weeks of every day socket use. These time points were chosen to enhance subject retention. Since we anticipate that one socket will be more comfortable than the other, it is possible that some subjects will find it challenging to use the less comfortable socket for a long period of time. By keeping each testing phase reasonably short (i.e., 6 weeks) we hope to retain as many subjects as possible. Additionally, by collecting data at 3 time points, we hope that if subjects are unable to continue to wear the socket for the entire six weeks, we will have initial and intermediate times points for comparison.

Step activity monitors attached to the test prostheses will allow monitoring of every day socket use. This will provide information regarding compliance with use of each prosthesis. As a secondary consideration, it will allow us to check whether there is a relationship between comfort and step activity.

When assessing the biomechanics of walking data consistency will be assured by (1) collecting all data in the same laboratory using the same instrumentation; (2) having marker placement conducted by the same experienced person who has been shown previously to have high reliability in this task; and (3) having a single person post-process all the data.

Since we hypothesize that the sub-ischial socket will be more comfortable than the standard-of-care ischial containment socket, it may be difficult to convince current wearers of the sub-ischial socket to revert to wearing an ischial containment socket every day for the time required by the study. It is also likely that those who have already adopted the sub-ischial socket will be particularly biased against the ischial containment socket, leading to larger differences in our primary endpoint. To account for this issue, we plan to recruit only those patients with no previous experience of the sub-ischial socket.

11.5 Handling of data study-wide:

PROTOCOL TITLE: Functional Performance Evaluation of the Northwestern University Flexible Sub-Ischial Vacuum (NU-FlexSIV) Socket for Persons with Transfemoral Amputation

Any electronic data maintained at NUPOC is on encrypted and password protected computers located in locked rooms and all paper files are stored in locked cabinets in locked rooms. Both computers and paper files are accessible only to NUPOC personnel.

The collaborating prosthetists will only create and use the forms required for recording the fitting and fabrication of their particular socket and these can be de-identified. Once the subject has completed that phase of the study, forms are given in person or by mail to the PI to collate with the main subject file to be held at NUPOC.

Data will be retained indefinitely. There are no plans to destroy the data.

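### The week-6 paired t-test on socket comfort implies a completer analysis: earlier scores go unused when a socket is stopped early, and no sensitivity analysis is planned

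*Combined protocol and SAP*

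**What the plan says.** - **Endpoint and test (11.1, Hypothesis 1).** "Our primary end point is Socket Comfort Score at 6 weeks", followed by "Hence, a matched pairs t-test" at alpha 0.05. No analysis set is named anywhere.
- **Missing data (11.1).** The planned step is descriptive: "we will describe the amount of data that are missing, and we will compare participants with and without missing data". The same paragraph says that cases will not be dropped and that other, unspecified approaches will be used if assumptions appear violated.
- **Sample size (11.2, 23.3).** 25 pairs are needed. "In order to account for possible attrition in subject numbers we will recruit 35 persons". Section 23.3 repeats that 25 of the 35 must complete.
- **Why three visits (11.4).** The first reason is accommodation: "Since accommodation to sockets is unknown, data will be collected at baseline", and again at 3 and 6 weeks. The second is retention, because "it is possible that some subjects will find it challenging to use the less comfortable socket for a long period of time". The plan's hope is stated as follows: "if subjects are unable to continue to wear the socket for the entire six weeks, we will have initial and intermediate times points for comparison".
- **Expected direction (11.4).** "we hypothesize that the sub-ischial socket will be more comfortable than the standard-of-care ischial containment socket", so the socket expected to be hard to keep wearing is the IC socket.

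**The concern.** A paired t-test on week-6 scores has no place for a subject who lacks one of the two scores. Read with the requirement that 25 complete, the plan implies an analysis of completers, although it never says so. Section 11.4 names discomfort as a likely reason for stopping, and comfort is the primary outcome, so the subjects who drop out of the test may differ systematically on the quantity being tested. The plan collects the data that could reduce the problem but gives no rule for using them: no model, imputation, carry-forward or earlier-visit comparison is specified.

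Two things are at stake. The estimate can be biased in a direction that depends on which socket is stopped more. And without a prespecified rule, the handling of early stops could be chosen after the scores are seen.

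**Working it through.** **1. The plan's own figure.** Inputs from 11.2: d = 0.754, two-sided alpha 0.05, target power 0.95. Power of the paired t-test is P(|T| > t(0.975, n−1)), with T noncentral t and noncentrality d√n. For n = 25, 0.754 × √25 = 3.77 and power is 0.951, so the stated 25 reproduces. The allowance is (35 − 25)/35 = 28.6%. This is a recruitment margin; no attrition rate is forecast. Power is 0.991 with 35 pairs, 0.979 with 30 and 0.892 with 20. Random loss within the allowance is therefore covered, and the remaining question is bias.

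**2. Who enters the test.** The statistic is mean(D)/(SD(D)/√n), with D = NU-FlexSIV week 6 minus IC week 6. If either score is missing, D does not exist, and the subject's week-1 and week-3 scores contribute nothing.

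**3. Size of the bias in completers (simulation).** Apart from the 35 subjects and the 28.6% allowance, every input is an assumption.
- Score = socket mean + subject + subject-by-socket + visit effect. SDs in that order: split A 1.0, 1.27, 0.63; split B 1.2, 1.0, 1.0.
- Paired SD = √(2 × (subject-by-socket variance + visit variance)): A √(2 × (1.27² + 0.63²)) = 2.005; B √(2 × (1 + 1)) = 2.000.
- Correlation between visits in one socket: A 0.87, B 0.71.
- True difference 1.5 (1.5/2 = 0.75, close to the plan's d) or 0.
- Stopping is logistic in the week-3 score, slope 0.5 to 1.5 per point, with the intercept set to the loss rate. One-socket cells use 20,000 trials each.

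Ranges cover both splits and all slopes. The last column is power when the true difference is 1.5 and two-sided type I error when it is 0.

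| Where the loss falls | Total loss | True difference | Mean estimate | Rejection rate |
|---|---|---|---|---|
| Equally in both | any tested | 0 | within 0.005 of 0 | 0.046–0.054 |
| NU-FlexSIV 2:1 | about 26% | 0 | 0.04–0.12 | 0.05–0.06 |
| IC 2:1 | about 26% | 1.5 | 1.38–1.46 | about 0.94 |
| NU-FlexSIV only | 10% | 0 | 0.05–0.15 | 0.05–0.07 |
| IC only | 10% | 1.5 | 1.35–1.46 | 0.96–0.98 |
| NU-FlexSIV only | 28.6% | 0 | 0.12–0.36 | 0.06–0.15 |
| IC only | 28.6% | 1.5 | 1.13–1.38 | 0.79–0.91 |

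For comparison, 25 subjects left at random give power 0.95.

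**4. A model using all visits.** Same assumptions, strongest dependence, all of a 28.6% loss in one socket, and subjects who stop in period 1 assumed never to receive the second socket (the plan does not say). A REML mixed model with unstructured covariance over weeks within a socket gives 1.50 (A) and 1.52 (B) for a true 1.5, with power 0.98. Its null bias is about 0. Its type I error is 0.053 in A; in B it was 0.066 in 1,500 trials and 0.042 in a further 1,750 (pooled 0.053). Those two runs differ by more than chance readily explains (z = 3.0), so read this as near 0.05, not exact.

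The covariance matters. If subjects also differ in trend over weeks (assumed SD 1.0 by week 6), this model keeps type I error at 0.044, while a model with random intercepts only gives 0.117.

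These cells are missing at random by construction, which favours the model. If stopping follows the unseen week-6 score, 0.12 to 0.31 points of bias remain against about 0.45 for completers. Type I error is then 0.07 to 0.16 against 0.19 to 0.22.

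**The case against.** The defence has real force on size. In the direction the plan expects (IC stopped more), the completer estimate is too small, so any error is against the new socket. A socket stopped twice as often as the other causes little harm, and at 10% loss even one-sided stopping barely moves type I error. The larger figures need the whole recruitment allowance spent in one socket and, for type I error, the direction the plan does not expect. All of this stands and limits the point.

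The textual defence is weaker. The promise not to drop cases follows the histogram and outlier check and does not say how an incomplete pair would be kept. The alternative approaches are triggered by violated assumptions, not by missing scores. Comparing participants with and without missing data is a diagnostic and leaves the estimate unchanged. Section 11.4 does show an intention to use the earlier scores; only the method is absent.

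It is also fair to say that comfort had wear continued is not the only sensible target for an abandoned socket. Counting a stop as a poor outcome, or using the last score while worn, can be defended too. That is a reason to state the target.

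Some stronger readings go beyond the documents:
- A reader might infer that the plan commits to excluding non-completers. It does not; this is an inference from the test and the sample size wording.
- A reader might infer that the expected stopping would manufacture a benefit for NU-FlexSIV. The expected direction does the opposite.
- A reader might infer from the reference to summary data in 11.3 that visit-level scores will not reach the statistician. That section concerns confidentiality, one score per visit is naturally summary data, and 10.1 sends de-identified data to the statistician.

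**Conclusion.** The gap is real and worth fixing before analysis, but it is not a fatal flaw. The stated primary test cannot use a subject without both week-6 scores, the plan itself links early stopping to comfort, and neither a rule for the earlier scores nor a sensitivity analysis is given.

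How much this matters turns on imbalance in stopping between sockets, which cannot be known in advance. The effect ranges from nothing (equal stopping), through minor (2:1), to material (all of a 28.6% loss in one socket). A reader might take the top of that range, type I error of 0.15, as the likely outcome. The documents do not support this, since they forecast neither that much loss nor loss in NU-FlexSIV alone.

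The sizes rest on assumed SDs, loss rates and strength of dependence, and on stopping that follows the week-3 score. Stopping that follows the unseen week-6 score would be worse for completers and only partly repaired by a mixed model.

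**What to change.** 1. **State the estimand** for a socket stopped early. The proposal here is week-6 comfort had wear continued; a different choice would need a matching analysis.
2. **For that estimand, make the primary analysis a REML linear mixed model** on all Socket Comfort Scores at weeks 1, 3 and 6 in both sockets. Fixed effects: socket, week, socket-by-week and period. Period is included because incomplete pairs no longer balance over the two periods. Use a covariance that lets subjects differ in trend within a socket, and Kenward-Roger degrees of freedom. The primary contrast is the week-6 socket difference at two-sided alpha 0.05, in every randomised subject with at least one score. Keep the paired t-test in completers as supportive.
3. **Record the reason for each missing week-6 score, and prespecify one sensitivity analysis** that treats a stop for discomfort or fit as a worse outcome. An example is a delta adjustment of the imputed week-6 score in the stopped socket only, with the tipping point reported. A grid of 0 to 3 points would span the 1-to-3-point sensitivity to socket change cited in 11.1. Its largest effect, before flooring scores at 0, is 3 × 10/35 = 0.86 points if all ten losses are discomfort stops in one socket.

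**Cost.** Analysis-plan wording, one reason-for-missing field and somewhat more analysis work. There are no new visits, and endpoint, alpha and sample size are unchanged. The downside is reliance on missing-at-random and covariance assumptions, which the sensitivity analysis can probe but not prove.
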